8.3.10 Special safety procedures

8.3.10.1 Serious adverse events of special interest

Amyloid Imaging Related Abnormalities (either ARIA-E or ARIA-H) and Aseptic Meningo-Encephalo-Myelitis have occurred in clinical trial of anti- β -amyloid immunotherapies and are considered as Serious Adverse Events. They should be reported as previously described.

In addition, a specific Decision Tree is set in place for the management of these SAEs, in case of occurrence see below:

Process for positive ARIA (ARIA-H and ARIA-E) findings

The results of the central MRI safety read will be made available to the Site and Sponsor prior to the next scheduled dose. The dose cannot be administered until the MRI results are received and approval is received from the MRI Central Reader. In the event of a positive ARIA (ARIA-H or/and ARIA-E) finding, the MRI Safety Review Committee, composed by i) the site IP, ii) the MRI central reader and iii) the study Medical Advisor (who will have access to the MRI data and central radiology reports) will review the Central Radiology read together with all other safety data available to the Sponsor determine the appropriate course of action. If there is a positive ARIA finding, then the subject will be asked to attend a follow-up scans at 2, 4, 6 and 12 months after the event in order to consider the ARIA finding resolved or clearly decreased and stabilized (as per the central read). Those scans are classified as “unscheduled” scans.

ARIA-H reporting

Any new micro-hemorrhage (1 or more) found in an MRI is an ARIA-H and needs to be informed to [REDACTED] Drug Safety either as a new SAE or Follow up SAE (Section 8.3.9), taking account of the following:

- If the total number of new micro-hemorrhage is greater than 3 (at any time during the study) in relation to V0, patients will stop the study medication regardless of number of events presented at screening visit.
- If the total number of new micro-hemorrhage is less than 3 (at any time during the study) in relation to V0, patients will NOT stop the study medication regardless of number of events presented at screening visit.

In addition and in order to consider an ARIA-H as a new event or progression of previous one, we will take in consideration the following:

- Any new micro-hemorrhage (1 or more) showed in the follow up MRIs and/or Protocol MRIs in a subject with previous ARIA-H will be consider a progression of previous ARIA-H if the patient DID NOT TAKE the study medication in between of MRI examinations. In such cases, a Follow up SAE will be completed with all information

(Follow up SAE will be completed, regardless of new findings, after a Follow Up MRI in order to keep [REDACTED] Drug Safety informed on the progression of patients).

- Any new micro-hemorrhage (1 or more) showed in the follow up MRIs and/or Protocol MRIs will be consider a NEW ARIA-H if the patient took the study medication in between of MRI examinations and in such case, a new SAE Report Form will be completed with all information required.

ARIA Thresholds and ARIA Decision

We propose this to be based in the guidelines published by the Alzheimer Association Research Roundtable Working Group (Sperling et al. 2011) as follow.

1. Patients developing mild ARIA-E or mild ARIA-H (≤ 3 incident micro-haemorrhages) without clinical symptoms could continue in the study.
2. Patients developing moderate or severe ARIA-E (as assessed by the MRI central reader) without clinical symptoms, or those with ARIA-E accompanied by mild clinical symptoms, will suspend treatment and resume once ARIA (and symptoms, if any) resolved.
For these patients, if ARIA appears at the MRI after the third shot and resolve within two months, they resume for the remaining two shots and booster; if ARIA does not resolve within two months then, they resume at the booster shot (m10) if resolved; otherwise, they permanently discontinue treatment.
3. Patients who develop ARIA-E or ARIA-H (≤ 3 incident micro-haemorrhages) accompanied by moderate, severe, or serious clinical symptoms, >3 incident micro-haemorrhages, any incident macro-haemorrhage, or >1 incident haemosiderosis at any time during the study will permanently discontinue treatment.

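### Protocol 8.3.10.1 gives opposite dosing orders for a patient with 1 or 2 new micro-haemorrhages and moderate or worse symptoms, and does not say which governs

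*Protocol*

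**What the plan says.** Protocol 8.3.10.1 introduces its ARIA rules with one sentence: "a specific Decision Tree is set in place for the management of these SAEs, in case of occurrence see below". Three blocks follow.

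- **Process for positive ARIA findings.** Dosing is held after each safety scan: "The dose cannot be administered until the MRI results are received and approval is received from the MRI Central Reader". For a positive finding, a committee of the site investigator, the central reader and the Medical Advisor "will review the Central Radiology read together with all other safety data available to the Sponsor determine the appropriate course of action".
- **ARIA-H reporting.** Two bullets use only the count of new micro-haemorrhages since V0. More than 3 means that study medication stops. The other bullet reads: "If the total number of new micro-hemorrhage is less than 3 (at any time during the study) in relation to V0, patients will NOT stop" study medication. Both add that the number present at screening is irrelevant, and neither mentions symptoms or other lesion types.
- **ARIA Thresholds and ARIA Decision.** Item 1 covers mild ARIA-E, or ARIA-H with 3 or fewer new lesions: such patients "without clinical symptoms could continue in the study". Item 2 covers moderate or severe ARIA-E without symptoms, "or those with ARIA-E accompanied by mild clinical symptoms, will suspend treatment and resume once ARIA (and symptoms, if any) resolved". Item 3 covers ARIA-E, or ARIA-H with 3 or fewer new lesions, "accompanied by moderate, severe, or serious clinical symptoms, >3 incident micro-haemorrhages, any incident macro-haemorrhage". Its last criterion and the order that applies to the whole item are: "or >1 incident haemosiderosis at any time during the study will permanently discontinue treatment".

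**The concern.** The bullet is phrased as a dosing instruction and has no exception for symptoms. Item 3 is also a dosing instruction, and it applies explicitly to ARIA-H with 3 or fewer lesions once symptoms are moderate or worse. The two overlap for a patient with 1 or 2 new lesions and such symptoms, and there they give opposite orders.

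ARIA is a serious adverse event of special interest in this trial, and 8.3.11.1 treats its occurrence as expected. A reader who follows the bullet errs in the unsafe direction, because a vaccine dose cannot be withdrawn once given. Sites could also handle like cases differently, which would blur the later account of why treatment stopped or continued after ARIA-H.

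**Working it through.** The protocol gives no figure to reproduce. The check compares the two sets of rules case by case.

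| New micro-haemorrhages since V0 | Other features | Reporting bullets | Decision list | Result |
|---|---|---|---|---|
| 1–2 | none | do not stop | item 1: could continue | agree |
| 1–2 | mild symptoms | do not stop | no rule (item 2 places mild symptoms with ARIA-E only) | one list silent |
| 1–2 | moderate, severe or serious symptoms | do not stop | item 3: permanently discontinue | **conflict** |
| 1–2 | macro-haemorrhage, or more than 1 haemosiderosis | do not stop | item 3: permanently discontinue | conflict only if read literally |
| 1–2 | ARIA-E that meets item 2 | do not stop | item 2: suspend, then resume | conflict only if read literally |
| exactly 3 | none | no rule | item 1: could continue | one rule only |
| exactly 3 | mild symptoms | no rule | no rule | **gap** |
| exactly 3 | moderate or worse symptoms | no rule | item 3: permanently discontinue | one rule only |
| more than 3 | any | stop | item 3: permanently discontinue | agree in direction |

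The gap at exactly 3 arises because one bullet covers fewer than 3 and the other more than 3. Item 1 requires no symptoms, and the symptom criterion in item 3 starts at moderate.

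**Is there a tie-breaker?** Four places could supply one.

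1. The Central Reader hold and the committee review (8.3.10.1) name who decides, not which list they should apply.
2. Section 5.3.2 permits withdrawal for related micro- or macro-haemorrhages but does not require it, and it refers back to 8.3.10.
3. Section 2.6 makes the absence of MRI safety issues a condition of entering Part B. It does not deal with findings during Part B.
4. SAP 1.1 gives the SAP primacy over the protocol for analyses only, not for dosing.

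None of these ranks the bullet against item 3.

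**Doses that a Part B finding would leave open.** Planned dose days are 0, 28, 56, 84, 112 and 294 (V1B, V4B, V7B, V10B, V13B, V18B). On-treatment MRIs fall on days 70 (V9B), 168 (V16B) and 280 (V17B).

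- Delayed-start group: after day 70, the doses on days 84, 112 and 294 remain, so 3 of 6 ABvac40 doses. After day 168 or day 280, only day 294 remains, so 1.
- Booster group: ABvac40 is given only at V13B (day 112). After day 70, that 1 ABvac40 dose and 2 placebo doses (V10B, V18B) remain. After day 168 or day 280, no ABvac40 dose remains.

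These counts describe one hypothetical patient. They do not estimate how many patients are affected.

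**The case against.** The best defence is structural. The bullet stands under a reporting heading, after a sentence about informing drug safety and before the rules that separate a new event from progression. Treatment thresholds have their own later heading, and a sensible reader would probably follow item 3. In addition, no dose is given without Central Reader approval, and every positive finding goes to a committee that sees all the safety data. That committee would also receive the case of exactly 3 lesions with mild symptoms. In Phase I (Section 2.2) there was no ARIA-E, and the one micro-haemorrhage was in a placebo patient. Section 8.3.11.1 says that ARIA is reported much less often with active vaccines.

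Most of this stands, and it limits the weight of the point. It does not remove the conflict: the bullet's words are about giving or stopping drug, and the committee receives two contrary instructions with no order of precedence.

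A reader might infer three stronger claims that the documents do not support.

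- *The bullet equally overrides the macro-haemorrhage and haemosiderosis criteria in item 3, and the item 2 suspension.* That holds only on a literal reading. A micro-haemorrhage count rule can fairly be read there as meaning that the count alone is no reason to stop. Only the symptom criterion concerns the same ARIA-H finding.
- *Patients would be dosed against item 3.* The dose hold and the committee stand in the way, and no frequency is given.
- *Part A doses were certainly still exposed under this version, signed on 10 July 2020.* The plan gives only September 2019 for last patient in. A first dose on 1 September 2019 puts V18 (day 294) on 21 June 2020, before that signature, so the planned dates do not establish it.

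**Conclusion.** The inconsistency is real but narrow. For 1 or 2 new micro-haemorrhages with moderate, severe or serious symptoms, Protocol 8.3.10.1 orders both continuation and permanent discontinuation, and nothing in either document says which prevails. There is also a small gap: exactly 3 new lesions with mild symptoms falls under no rule.

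This should be fixed because a stated dosing rule contradicts a safety stopping rule and the remedy is cheap. It does not merit a higher rating: safeguards apply to every positive scan, and no endpoint, error rate or analysis set is shown to depend on it. The number of patients affected is not estimated, because the documents give no rate of symptomatic ARIA-H. The conclusion assumes that the reporting bullets mean what they say about study medication. If they were meant only for counting and reporting, the text should say so.

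**What to change.** Make three changes in 8.3.10.1.

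1. State that items 1 to 3 of the ARIA decision list govern treatment.
2. Replace the second bullet with: *3 or fewer new micro-hemorrhages in relation to V0: study medication is not stopped on count alone, provided there are no clinical symptoms and no item 2 or item 3 criterion is met.* This aligns the cut-off with item 1.
3. Add a default for ARIA-H with 3 or fewer new lesions and mild symptoms, including exactly 3: hold the dose until the MRI Safety Review Committee decides. Without it, the first two changes would leave this case with no rule.

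The cost is a short text change and a note to sites and the Central Reader. The downside is a possible dose delay for mildly symptomatic patients. No new data are needed for the action taken with study drug, which the adverse event form already records (8.3.8).

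If dosing has ended, report in the clinical study report the symptom grade and the action taken for each ARIA-H case with 3 or fewer new lesions.

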8.3.10.2 Reactions to the vaccine

Reactions to the vaccine may vary from mild to severe reactions (shock or anaphylaxis) that can cause death. If such a severe reaction is suspected, patients will be observed for 24 hours in the study center after administration of the vaccine (overnight hospitalization) and before being discharged vital signs and a thorough examination will be recorded to assess any reaction to the vaccine (see Appendix 1).

8.3.11 Reference safety information

8.3.11.1 Expected Serious Adverse Drug Reactions

Expected serious Adverse Drug Reactions (ADR) to ABvac40 are Amyloid Imaging Related Abnormalities (ARIA) either ARIA-edema (ARIA-E) or ARIA-hemorrhagic (ARIA-H).

ARIA-E is the most frequent SAE occurring in clinical trial involving passive immunotherapies with monoclonal antibodies targeting A β peptides. Incidence of ARIAs appeared to depend, among other factors, on the drug product characteristics and dosing but can affect a relevant proportion of the participants (up to 50% in some cases). Although ARIAs have been much less frequently reported after active immunization of patients with vaccines against A β peptides (in particular, not cases of ARIA-E or ARIA-H occurred during ABvac40

phase I clinical trial), their occurrence in this phase II is deemed as expected and a specific protocol is set in place to managing this serious Adverse Drug Reaction.

All Expected serious ADRs must be submitted to expedited safety reporting using the designated SAE Report Form and the procedure described in the Clinical Trial Protocol (see section 8.3.9), and must be accompanied with the corresponding MRI report available.

8.3.11.2 Unexpected Serious Adverse Drug Reactions

All other SAEs considered as potentially related with the investigational medicinal product (IMP), including Aseptic Meningo-Encephalo-Myelitis and systemic reactions to the vaccine (see appendix 1) should be considered as unexpected and submitted to expedited safety reporting using the designated SAE Report Form and the procedure described in the Clinical Trial Protocol (see section 8.3.9).

8.4 Type and Duration of the Follow-Up of Subjects after Adverse Events

In so far as is possible, all individuals will be followed up until the AE or suspected ADR has been resolved. If an AE/suspected ADR/SAE is present when the subject has completed the study, the course of the event must be followed until the final outcome is known, or the event has been stabilized and no further change is expected and the Investigator decides that no further follow-up is necessary.

9 STATISTICS

9.1 Statistical Methods

Unless otherwise specified, descriptive statistics will include the number of observations, number of missing values, mean (95% CI), standard deviation (SD), median, minimum, Q1, Q3 and maximum values for the continuous/quantitative data or absolute and relative frequency counts and percentages for categorical/qualitative data.

Individual patient data will be listed.

Data handling and evaluation procedures will be described in the Statistical Analysis Plan.

9.1.1 Demographic and Baseline Characteristics

Demographic and baseline characteristics will be summarized by treatment in the overall group and according to a-PET status (a-PET+ and a-PET-). For quantitative variables the number of observations, number of missing values, mean (95% CI), SD, median, Q1/Q3 and minimum/maximum will be provided. For qualitative variables, the frequency and percentage will be provided. Demographic variables will be compared between treated and placebo groups as correspond (Mann-Whitney or Chi square).

9.1.2 Efficacy Analysis (Part A)

9.1.2.1 Primary Efficacy Analysis (immunogenicity)

The primary variable for immunogenicity is the average maximal increment ($M\Delta$) of anti- $A\beta$ 40 antibody signal (OD in ELISA).

For the comparison of the response to treatment between the verum and placebo group the maximal increment ($M\Delta$) of anti- $A\beta$ 40 antibody signal (OD in ELISA) with regard to the pre-treatment visit (either V0 or V1) in each subject will be used as a summary measure. The treatment comparisons will be carried out by one-sided t test or Mann-Whitney U test if variable has non-normal distribution.

The trial will be considered successfully confirmatory regarding efficacy (immunogenicity) of ABvac40 if the average maximal increment ($M\Delta$) of anti- $A\beta$ 40 antibody signal (OD in ELISA) in the verum group is >0 OD than the average $M\Delta$ in the placebo group. This primary efficacy analysis will be conducted in the overall study population.

- Null hypothesis: The average maximal increment ($M\Delta$) of anti- $A\beta$ 40 antibody signal (OD in ELISA) for the treated group is equal to that for placebo.
- Alternative hypothesis: The average maximal increment ($M\Delta$) of anti- $A\beta$ 40 antibody signal (OD in ELISA) for the treated group is >0 OD than the average $M\Delta$ in the placebo group.

The $M\Delta$ of anti- $A\beta$ 40 antibody signal between the two treatment groups will be compared using an Analysis of Covariance (ANCOVA) model, using the $M\Delta$ as the dependent variable, baseline anti- $A\beta$ 40 antibody signal (OD in ELISA) as covariate and the treatment group and

amyloid positivity as fixed effects. In addition, the number and percentage of patients in each visit reaching a value greater or equal than the $M\Delta$ will be tabulated by groups for each variable.

Patients in the verum group will be classified as “Positive Responders” when: i) their $M\Delta$ of anti-A β 40 antibody signal is equal or greater than 3 times the standard deviation of the titration ELISA and ii) more than the 50% of the signal in the visit reaching the $M\Delta$ is eliminated by pre-adsorption of the sample. The antibody titers, defined as the inverse of the maximal plasma sample dilution which showed an OD increase ≥ 3 SD with regard to the pre-immune sample (either V0 or V1), of “Positive Responder” will be reported.

9.1.2.2 Secondary Efficacy Analysis

The trial will be considered satisfactory if the difference of the average maximal increment ($M\Delta$) of anti-A β 40 antibody signal (OD in ELISA) in the treated group is > 1.778 OD than the average $M\Delta$ in the placebo group; the difference that was reached between both groups in the phase I clinical trial of ABvac40.

The secondary efficacy variables regarding assessment of disease biomarkers and cognition (see section 7.1) will be analyzed descriptively in the overall group and separately in the amyloid-PET negative (verum and placebo) and the amyloid-PET positive (verum and placebo) subjects pertaining to the ITT and PP populations

For the exploratory comparison of the secondary efficacy variables for the characterization of the immune response (section 7.1.2) between the verum and placebo group, the maximal increment ($M\Delta$) with regard to the pre-treatment visit (either V0 or V1) in each subject will be used as a summary measure for each of the following variables: i) the OD signal for plasma peptides and cytokines levels, or A β plasma levels as determined by LC-MS, ii) the relative number of cells subsets from peripheral blood mononuclear cells; and iii) the number of cytokine and antibody producing cells. Statistical comparison between groups of treatment will be done for the variable $M\Delta$ by means of ANCOVA models, using the $M\Delta$ as the dependent variable, baseline as covariate and the treatment group and amyloid positivity as fixed effects. In addition, the number and percentage of patients in each visit reaching a value greater or equal than the $M\Delta$ will be tabulated by groups for each variable.

Mixed-model repeated-measures (MMRM) analyses will be performed for all the primary and secondary efficacy variables (section 7.1) to assess between-group differences in change scores from baseline (V0/V1) to Int-6m (V16), V21 and to the final visit (V25). The dependent variable in each MMRM analysis will be “change from baseline”. Fixed effects will include baseline scores on outcome measures, age at baseline, group assignment, amyloid positivity, study visit, and treatment-by-visit interaction. Additionally, covariates that are significantly associated with the response measure ($p < 0.15$) and are out of balance at baseline ($p < 0.2$) will be included as fixed effects. Variables considered as potential covariates in each model will be demographic variables, baseline characteristics, general treatment for AD and concomitant medication.

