- Number of withdrawn patients, number of patients who discontinued from treatment and reasons for withdrawal and discontinuation, respectively
- SAEs and AEs
- Rate (%) AEs
- Expected serious adverse drug reactions like Amyloid Related Imaging Abnormalities
- Physical and neurological examination significant abnormal findings
- Concomitant medication
- Vital signs (blood pressure, heart rate, respiratory rate, body temperature) and body mass index (weight, height) values.
- Safety Brain MRI
- Key EKG parameters
- Analytical haematology, toxicology (reactive protein), biochemistry, coagulation, serology and urine test strip results (all data regardless if they are abnormal).
- Average maximal increment ($M\Delta$) of anti-A β 40 antibody signal (OD in ELISA) (all meetings)
- A β 40 & A β 42 in plasma (all meetings)
- RBANS total score (all meetings)
- Results of futility analysis and sample size re-estimation (all meetings)

After each formal data evaluation meetings, the DSMB will provide recommendations to the Sponsor mainly in the following areas:

- Suspension of recruitment pending further safety review, if data received suggest significant adverse effect of the investigational medicinal product.
- Stop the study due to efficacy concerns (futility)*:
 - If, given the data up to the meeting's cut-off date, the futility analysis, based on the primary efficacy analysis (confirmatory) of superiority (meaning that the average maximal increment [$M\Delta$] of specific anti-A β 40 antibody signal [OD in ELISA] for the treated group is >0 OD to that of placebo group), yields a conditional power of less than 20% the DSMB will recommend to stop the study. Details on the futility analysis will be given in the DSMB SAP.

**A safety and efficacy reviews will be taken into account in order to make a recommendation*

- Increase the sample size based:
 - If pooled SD for the average maximal increment ($M\Delta$) of anti-A β 40 antibody signal (OD in ELISA) is higher than the estimated 1.6 (according to the results of the Phase I study), the DSMB will recommend to the sponsor to increase the sample size according to the observed pooled SD, to ensure at least 80% power to detect a treatment superiority with margin of 1.778 in average maximal increment (as considered in the secondary efficacy analysis [satisfactory])

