9.3 Level of Significance to Be Used

The statistical tests will be performed with a 2.5% significance level for the primary efficacy (immunogenicity) variable and 5% for the and will be one-sided for the primary variable of biological activity and two-sided for the secondary biological activity/efficacy variables. In addition to the tests, 95% CI will be reported.

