6.1.2 Sensitivity Analyses for Primary Outcome

No adjustments will be made for multiple testing of study parameters. Therefore, interpretation of p-values for these sensitivity analyses should be considered descriptive in nature.

The following analyses will be performed for the primary outcome:

1. The primary analyses will be repeated for the PP Analysis Set.
2. The primary analysis (t-test) will be repeated, using the mITT Analysis Set to test the hypothesis:
 - Null hypothesis: average $M\Delta$ anti- $A\beta$ 40 (ABvac40) - average $M\Delta$ anti- $A\beta$ 40 (placebo) ≤ 1.778
 - Alternative hypothesis: average $M\Delta$ anti- $A\beta$ 40 (ABvac40) - average $M\Delta$ anti- $A\beta$ 40 (placebo) > 1.778
3. The change in anti- $A\beta$ 40 antibody signal from baseline to each post-baseline efficacy visit will be analyzed using a Mixed-Model Repeated Measures (MMRM), using the mITT Analysis Set.

The MMRM will include change from baseline in anti- $A\beta$ 40 antibody signal as the dependent variable; treatment, protocol-specified visits, treatment-by-visit interaction, and amyloid positivity as the fixed effects; baseline anti- $A\beta$ 40 antibody signal and baseline age as covariates; and measures within-patient at each visit as a repeated measure. The variance-covariance matrix will be assumed to be unstructured. If the procedure does not converge then a compound symmetric variance-covariance matrix will be used instead.

The least squares (LS) mean change from baseline will be presented for each treatment group (ABvac40 and placebo) for each post-baseline scheduled visit, along with the LS mean treatment difference (ABvac40 – placebo), 95% CI for mean treatment difference and p-value for comparison of treatment groups.

The following is sample SAS® code for the MMRM:

```
proc mixed data=pp method=ml;
  class Patient Treatment Visit a_PET;
  model change = Baseline a_PET Treatment Visit age
    Treatment*Visit / s;
  repeated Visit / type=un subject=Patient r;
  lsmeans Treatment*Visit / pdiff cl;
run;
```

A plot of LS means over time will be presented by treatment group.

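### The 'satisfactory' claim at 1.778 OD has no settled decision rule: the protocol attaches no test where it states the claim, and the SAP tests the margin only descriptively

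*Protocol*

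**What the plan says.** **Primary claim.** Protocol 9.1.2.1 calls the trial successfully confirmatory if the difference in average maximal increment is above 0 OD. It states null and alternative hypotheses and names the method: "The treatment comparisons will be carried out by one-sided t test or Mann-Whitney U test". Protocol 9.3 sets 2.5% for this variable and describes the tests as "one-sided for the primary variable of biological activity and two-sided for the secondary biological activity/efficacy variables".

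**Second claim.** Protocol 9.1.2.2, and in the same terms Protocol 4.1.1 and the synopsis, calls the trial 'satisfactory' if the difference "in the treated group is > 1.778 OD than the average $M\Delta$ in the placebo group". The benchmark is "the difference that was reached between both groups in the phase I clinical trial of ABvac40". None of the three places gives hypotheses, a test, a level or a confidence bound for this claim.

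**The same criterion elsewhere in the protocol.** Protocol 9.1.5.1 aims the sample-size increase at "at least 80% power to detect a treatment superiority with margin of 1.778 in average maximal increment". A parenthesis there points back to the secondary efficacy analysis and repeats the 'satisfactory' label.

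**SAP.** Item 2 of SAP 6.1.2 reads "The primary analysis (t-test) will be repeated, using the mITT Analysis Set to test the hypothesis" and sets a null of a difference of at most 1.778. It stands among the sensitivity analyses, and the section opens by saying that "interpretation of p-values for these sensitivity analyses should be considered descriptive in nature". The available SAP text does not use the word 'satisfactory'. SAP 9.2 records changes to the analysis sets, one added outcome and the variables not analysed, but nothing on this criterion. SAP 1.1 gives the SAP precedence over the protocol where analyses differ.

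**The concern.** The protocol makes two trial-level claims on one endpoint, and only the first has a stated decision rule. For the second, the literal wording needs only the estimate to pass 1.778, the DSMB section speaks of a margin, and the SAP runs a margin test without attaching any conclusion to it.

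The label says that the trial beat the Phase I result, and Protocol section 2 describes these data as crucial to the Phase III go/no-go decision. If the trial succeeds on the primary test with an estimate somewhat above 1.778, a reader of the protocol could call it 'satisfactory', while a reader of the SAP would see a non-significant descriptive p-value and no statement about the label.

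**Working it through.** **Inputs**
- SDs 2.0 (active) and 1.0 (placebo), difference 1.778, one-sided level 0.025: Protocol 9.2 and SAP 3.2.
- Per arm: 60 randomised and 35 expected completers (Protocol 9.2); 15 as the stated minimum for 85% power (Protocol 2.6).
- Analysis set for item 2: mITT, which needs a baseline and at least one post-baseline OD (SAP 3.1.2). Its size should therefore be closer to 60 than to 35 per arm.
- Assumption: SAP 6.1.2 does not restate the level, so 0.025 is taken from the primary t-test that item 2 repeats.

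**Step 1. Reproduce the plan's own power figure (null of 0)**

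SE = √((2.0² + 1.0²)/n).
- n = 15: SE = √(5/15) = 0.577. 1.778/0.577 = 3.08, so normal-approximation power is Φ(3.08 − 1.96) = 86.9%. The t-test gives 84.4% (pooled df) or 83.5% (Welch df).
- n = 35: t-test power 99.6%.

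This agrees with the stated 85% with 15 per group, and with more than 85% with 70 completers. That power is against a null of 0 and says nothing about the 1.778 claim.

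**Step 2. Smallest observed difference that rejects a null of at most 1.778**

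Threshold = 1.778 + t(0.975, df) × SE, with Welch df = (n − 1) × 25/17.
- n = 60: SE = √(5/60) = 0.289, df = 86.8, t = 1.988. Threshold = 1.778 + 0.574 = **2.35**.
- n = 35: SE = √(5/35) = 0.378, df = 50.0, t = 2.009. Threshold = 1.778 + 0.759 = **2.54**.

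Pooled df gives 2.350 and 2.532. Using the 1.6 pooled SD from Protocol 9.1.5.1 in both arms gives 2.356 and 2.541. At one-sided 0.05 the thresholds would be 2.26 and 2.41.

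**Step 3. How often each reading is met**

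Literal reading: 1 − Φ((1.778 − D)/SE) for true difference D. Margin test: noncentral t with Welch df, one-sided 0.025.

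| True difference D | n per arm | Literal reading | Margin test |
|---|---|---|---|
| 1.5 | 60 | 17% | 0.2% |
| 1.5 | 35 | 23% | 0.4% |
| 1.778 | either | 50% | 2.5% |
| 2.2 | 60 | 93% | 30% |
| 2.2 | 35 | 87% | 19% |

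The margin test reaches 80% power only at a true difference of about 2.60 (60 per arm) or 2.86 (35 per arm).

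**The case against.** The strongest reply is that the protocol, read as a whole, already means a test. Protocol 9.1.5.1 describes the criterion as "treatment superiority with margin of 1.778 in average maximal increment" and ties it to the 'satisfactory' label. The primary rule uses the same form of words with 0 in place of 1.778, and it is plainly a t-test. On that reading SAP item 2 is the intended analysis and no zone of disagreement exists. This largely stands: a reader might infer that the protocol lays down a point-estimate rule, and the documents do not support that. They support ambiguity, because the sentence that makes the claim carries no test.

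A reader might also infer that protocol and SAP give opposite verdicts on the same data. They do not, because the SAP attaches no verdict to item 2.

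Nor is the analysis itself open to choice after the result is known. The SAP takes precedence, is to be final before database lock, and fixes the hypotheses, test and analysis set. What it leaves open is the label.

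On the level, Protocol 9.3 can be read either way for a primary variable used in a secondary analysis, and its 5% clause is incomplete in the available text. One-sided 2.5% and two-sided 5% share the same upper tail of 0.025.

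Finally, secondary efficacy objectives are labelled exploratory, neither the futility rule nor the Part B stopping criteria use the label, and 50% at the threshold is a property of any point estimate. All of that is true and limits the importance of the point. It does not explain why a protocol-level success statement should lose its standing with no entry in SAP 9.2.

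**Conclusion.** The point holds as a conflict over a stated success claim. Protocol 4.1.1, 9.1.2.2 and the synopsis declare the trial 'satisfactory' above 1.778 OD without a rule. Protocol 9.1.5.1 treats the criterion as a margin. The SAP runs the margin test descriptively and is silent on the label.

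Observed differences from just above 1.778 to about 2.35 OD (60 per arm, closest to mITT), or to about 2.54 OD if only 35 per arm contribute, would be 'satisfactory' under the literal wording but not significant in the SAP's test. The range rests on the planning SDs, the analysed numbers and the assumed one-sided 0.025 level, and it will move with the observed SDs. It disappears if a margin test is accepted as the meaning of the claim. The primary confirmatory test is unaffected under every reading.

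**What to change.** Amend SAP 6.1.2 item 2, add a matching entry to SAP 9.2 and, if the protocol is amended, align Protocol 9.1.2.2 (and its repeats in 4.1.1 and the synopsis). Choose one option:

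- **(a) Keep the label.** Declare 'satisfactory' only if the primary test succeeds and the lower limit of the two-sided 95% CI for the difference in mean maximal increment (mITT) exceeds 1.778 OD. Move item 2 out of the sensitivity analyses, so that the descriptive-p-value sentence no longer covers it. No alpha split is needed: with the same t-test, (d − 1.778)/SE above the critical value implies that d/SE is above it too, so rejecting at most 1.778 implies rejecting at most 0.
- **(b) Drop the label.** Withdraw 'satisfactory' and report the difference with its 95% CI against the Phase I benchmark.

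Either option needs wording only, with no new data. The cost of (a) is that the label becomes harder to earn: a 2.5% chance if the true difference equals 1.778, against 50% under the literal wording. The cost of (b) is losing the claim.
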